Type 2 Diabetes (T2D) is a significant problem in older adults and is known to increase the risk of future frailty. More than 25% of the U.S. population aged \geq 65 years has T2D; and, recent projections suggest that the number of cases of diagnosed T2D in those aged \geq 65 years will increase by 4.5-fold (compared to 3-fold in the total population) between 2005 and 2050. Although the burden of T2D is often described in terms of its impact on working-aged adults, the disease also affects longevity, disability, and common geriatric syndromes such as frailty, which ultimately leads inability to maintain independence. The combination of the T2D epidemic and increasing population of older adults call for innovative healthcare strategies and communication technology such as mobile health (mHealth) that can play a significant role in modifying the lifestyle behaviors of older adults in order to improve frailty characteristics and manage T2D. It has been supported that mHealth can facilitate behavior promotion (diet, physical activity), improve self-management, self-efficacy, and medication adherence in older adults. Research indicates that older adults have positive attitudes toward the use of mHealth interventions and applications and confident in their ability to self-manage their T2D suggesting that the benefits of technology outweigh the costs of adapting its use in this population. To the best of our knowledge, no study has reported on the impact of behavioral lifestyle interventions for overweight/obese older adults with T2D on improvements of frailty characteristics. For this pilot study, we will conduct a randomized controlled trial to determine the feasibility and compare the preliminary efficacy of a behavioral lifestyle intervention and its impact on frailty-related measures in overweight/obese community-dwelling older adults with T2D. We will be using mHealth tools to enhance self-monitoring of multiple behaviors (diet and physical activity) and to manage T2D. Our overall goal is to test the hypothesis that the implementation of behavioral lifestyle interventions to promote physical activity and dietary modifications will help older adults with T2D to improve frailty characteristics and manage the disease, which may eventually lead to healthy aging. Such intervention would include the use of self-monitoring of diet and physical activity.

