$\Box \textbf{Dose escalation} \begin{array}{c} If yes, details \\ \rightarrow \end{array}$											-							
	$\Box \textbf{Dose ranging} \begin{array}{c} If yes, details \\ \rightarrow \end{array}$																	
	$\Box \textbf{Sub-studies} \begin{array}{c} If yes, details \\ \rightarrow \end{array}$																	
	5.3. Other Design Details : This will be a 6-month randomized controlled trial. The study will start after the approval from UT Health San Antonio IRB department. All study visits will be performed in the UT Health School of Nursing.																	

6. Study Population:		
6.1. Study Population(s)	6.2. Identify the criteria for inclusion	6.3. Identify the criteria for exclusion
Label/Name	The criteria that every potential participant must satisfy, to qualify for study entry.	The characteristics that make an individual ineligible for study participation.
To add more populations – select a row, copy & paste	All individuals in this study population must meet all of the inclusion criteria in order to be eligible to participate in the study	All individuals in this study population meeting any of the exclusion criteria at baseline will be excluded from study participation.

3

٧

Overweight/obese community-		Jnsafe to walk using EASY criteria or				
dwelling older adults with T2D	5	clinical judgement of the PI.				
	Men and women of all ethnic groups H	History of severe psychiatric disorders				
	Self-reported of provider-diagnosed with o	or cognitive impairment which interferes with active participation in				
	T2D for at-least 6 months.					
	Received basic diabetes self-	the study				
	management education R	Residence of long-term care facility				
		History of substance abuse in the past				
		/ear				
	the next 6 months.	Unwilling to be randomized in a				
	Overweight/obese (BMI ≥25 kg/m2 m	mHealth+ individual intervention group				
	Able to read and write in English					
	Own a smartphone					
	At PI discretion, participant is					
	willing/able to comply with the					
	protocol requirements					
6.4.	⊠ No □ Yes If yes, descr	ribe criteria below ↓				
Will screen failures be allowed						
to re-screen at a later date?						

7. Study Intervention(s) being tested or evaluated

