This can include prevention, diagnostic or therapeutic interventions (e.g., drug or device) or educational, health services or basic science interventions (e.g., educational program, health care delivery model, or examining basic physiology)

Behavioral lifestyle intervention: Participants (N=40) will be randomized to the mHealth+ group Intervention group (Group A; n=20) and mHealth+ individual intervention group (Group B; n=20) group using a block randomization table. (1) The mHealth+ group Intervention group (Group A) will receive a modified Look AHEAD behavior lifestyle intervention with smartphone-based self-monitoring of diet and physical activity. This comprises ten group sessions for lifestyle intervention in 6-months. The group will receive three weekly classes in the first month and then bi-weekly classes for month 2-3, and three monthly session in month four, five, and six. The frequency and layout of these classes will allow participants to master new skills gradually, then eventually wean off, and adopt the modified lifestyle as the part of their daily lives. (2) The mHealth+ individual intervention group (Group B) will receive an abbreviated behavior lifestyle intervention with smartphone-based self-monitoring of diet and physical activity in one face-to-face individual session at the beginning of the study. In addition, participants will receive self-study materials, from Look Ahead modules, and a monthly follow-up phone calls for the duration of the study (6-months). The goal for these follow up phone calls are to assess understanding of the modules, to promote continued engagement with the study material, and to provide clarification on materials as needed. Participants in the mHealth+ group Intervention group (Group A) and mHealth+ individual intervention group (Group B will receive instruction on how to download an app to help them record their diet and physical activity at the beginning of the study. (see updates to study protocol dated below)

Fitbit offers a simple, easy-to-use tool for tracking food and physical activity. It helps set daily calorie budget, and set and work towards goals for nutrient intake, weight loss, exercise, and more. https://www.fitbit.com/inspire

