04.12.20: Due to COVID-19 and social distancing order, we are adding hemoglobin Hba1c home test for our eight participants who are finishing the study on April 20, 2020. We have called all 8 participants and informed them about Hba1c home testing kit that will be delivered to their house after the final and tenth virtual session on April 20, 2020. We have confirmed their home address over the phone to mail the kit. Participants have been informed that the PI will explain and run the test individually with all 8 participants. Our next study group will finish the study in 2nd week of June, 2020. We will continue to follow our study participants and provide monthly behavioral educational sessions

4

in the group intervention, virtually, until the social distancing order will be lifted. Our study is not enrolling any new participants at this time.

On April 20, 2020, eight participants will finish the study and we will collect focus group questions virtually. We will also collect their individual questionnaire virtually to collect end of study assessments. Once the social distancing order will lift, we will collect face to face blood test and frailty assessments.

10.20.20: we finished our participants (N=20) in the group intervention and due to COVID-19 restrictions we were not able to enroll our participants for the control group (Group B). We talked with IRB staff and study team and decided to stop enrolling participating for the control group (group B) as the risk was higher based on the inclusion criteria for our study participants than the benefits for the control participants. Modification due to Pandemic, forgoing control arm, and worked with the interventional participants still worked with the study data to meet study aim-the deviation related to COVID-19 did not impact subject rights, safety, welfare, or the overall integrity of the science of the study.

8. Protocol-Directed procedures, items, services or tests

List all procedures directed by the study plan - including items or services provided as part of routine or conventional care and those needed to diagnosis or treat research related complications.

Important Note – The protocol directed procedures listed must match those in the Schedule of Activities (attachment) 8.1. Drugs (trade and generic, dosage, route of administration)

N/A

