8.4. Laboratory Tests

Laboratory tests: Complete blood count, chemistry with liver function tests, lipid profile, HbA1c, and inflammatory markers (CRP, IL6) will be collected from all participants. Approximately 28 ml of blood will be collected at baseline and at end of study for clinical labs and quantifying proteins of interest. Approximately 16 ml of blood will be collected in a serum separating tube and will be used for clinical lab values (complete metabolic panel, lipids and A1c). The remaining 12 ml of blood will be collected in an EDTA tube and will be used to quantifying circulating cytokines.

04.12.20: Due to COVID-19 and social distancing order, we will be adding hemoglobin Hba1c home test for our eight participants who are finishing the study on April 20, 2020. We will continue to our virtual behavioral education session and will collect other end of study assessments virtually.

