10.1. Measures to Minimize Bias: Randomization and Blinding

This section should contain a description of randomization and blinding procedures (if applicable to the study design). It should include a description or a table that describes how study participants will be assigned to study groups, without being so specific that blinding or randomization might be compromised. Plans for the maintenance of trial randomization codes and appropriate blinding for the study should be discussed. The timing and procedures for planned and unplanned breaking of randomization codes should be included. Include a statement regarding when unblinding may occur and who may unblind. Provide the criteria for breaking the study blind or participant code. Discuss the circumstances in which the blind would be broken for an individual or for all participants (e.g., for serious adverse evets (SAEs)). Indicate to whom the intentional and unintentional breaking of the blind should be reported.

The PI will not be blinded by the study mHealth+ group Intervention group and mHealth+ individual intervention group.

Participants (N=40) be randomized into two groups using a block randomization table to receive behavioral lifestyle educational intervention. Everyone will receive a baseline and end of study visits.

We divided our future participants into 4 groups (10 - (group A):10- (group A):10- (individual B):10 (individual B) and with the help of computer generated program, we will start our intervention group (Group A - n=20) first followed by our control group (Group B - n=20). (see updates dated below)

Participant in mHealth + group intervention (Group A) you will receive a total of 10 group sessions in 6-months. The group will receive 3 weekly classes in the first month and then bi-weekly classes for month 2-3, and three monthly session in month four, five, and six.

10.20.2020: we completed up to three face to face group intervention sessions (Group A) over WebEx due to COVID-19 restrictions.

10.20.20: we finished our participants (N=20) in the group intervention and due to COVID-19 restrictions we were not able to enroll our participants for the control group.

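### Section 12 was not updated after Group B was dropped: with 20 versus 0 participants its intervention term cannot be estimated, and no single-arm analysis is given

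*Combined protocol and SAP*

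**What the plan says.** All references are to the combined protocol and SAP.

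- **Design.** Section 2: "we will conduct a randomized controlled trial to determine the feasibility and compare the preliminary efficacy of a behavioral lifestyle intervention". Section 5.3: "This will be a 6-month randomized controlled trial". These two places give neither the number 40 nor a block table, and neither points to a later update. Section 7 gives the numbers: "Participants (N=40) will be randomized to the mHealth+ group Intervention group (Group A; n=20) and mHealth+ individual intervention group (Group B; n=20"). Section 10.1 has "Participants (N=40) be randomized into two groups using a block randomization table". Sections 7 and 10.1 both direct the reader to dated updates.
- **Order of starting.** Section 10.1 lists four sets of ten, two for Group A and then two for Group B, and adds "we will start our intervention group (Group A - n=20) first followed by our control group (Group B - n=20").
- **What happened.** The 10.20.20 update in Section 7 says the 20 group-intervention participants finished and "due to COVID-19 restrictions we were not able to enroll our participants for the control group (Group B"). Section 10.1 repeats this. Both sections say that the deviation left the science of the study intact.
- **Conduct in the pandemic.** Section 10.1 reports up to three group sessions held on WebEx. For eight participants finishing on April 20, 2020, the 04.12.20 updates add a home HbA1c test. Section 7 says "Once the social distancing order will lift, we will collect face to face blood test and frailty assessments"; Section 8.4 says "We will continue to our virtual behavioral education session and will collect other end of study assessments virtually".
- **Analysis.** Sections 12.3 and 12.4 give the same model text, with no dated update. Frailty status and score are modelled by a proportional odds cumulative logit (POCL) model on exposure to the intervention, adjusted at first only for baseline frailty status. A further model adds age, sex, ethnic group, BMI and HbA1c to look for interactions with the intervention. Fasting glucose, HbA1c and BMI get linear regression with intervention among the predictors. SPPB and PROMIS also go to the POCL model.
- **Use of the result.** Sections 12.2 and 12.4 intend to size a larger study from the intervention's effect on frailty category or score.

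**The concern.** The dated updates turn a two-arm comparison into a study of one arm, but the analysis section still belongs to the two-arm comparison. An intervention term needs people with and without the intervention, and here everyone analysed had it.

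Three things are at stake. The primary outcome has no analysis that can be run to give what it promises, and whatever replaces it will be chosen after Group A finished. The no-impact statement may be taken to cover the efficacy comparison announced in Section 2, which no longer exists. And a before-after change could be passed to the next trial as though it were a difference between groups.

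**Working it through.** **Inputs.** Group A 20, Group B 0 (updates in Sections 7 and 10.1). Model terms from Section 12.4. Section 12.2 declines a power analysis and gives 20 in Group A as a judgement, so the plan has no calculated figure to reproduce.

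**Step 1: the POCL model.** Let x be the intervention indicator and z the baseline covariates:

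logit P(Y ≤ j) = α_j − βx − γ′z.

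With x = 1 for all 20, this is (α_j − β) − γ′z. Adding any constant to β and to every α_j leaves the likelihood unchanged, so β is not identified. An interaction δ′(xz) becomes δ′z, so only γ + δ is identified.

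**Step 2: the linear models.** The same holds: with x = 1, only intercept + β is identified.

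**Step 3: numerical check.** Rank of the design matrices, with three baseline frailty levels, binary sex and two ethnic groups (the last is an assumption; an intercept column stands in for the cut-points):

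| Model | Columns | Rank at 20 v 20 | Rank at 20 v 0 |
|---|---|---|---|
| Initial POCL | 4 | 4 | 3 |
| Adjusted POCL, linear | 9 | 9 | 8 |
| With five interactions | 14 | 14 | 8 |

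With k ethnic groups, the adjusted model has 9 + (k − 2) columns and is always one short. The interaction model is short by 6 + (k − 2). The conclusion does not depend on k.

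**Step 4: can the text be read as a before-after plan?** It mentions the period from baseline to follow-up, but baseline frailty enters as a covariate. The outcome is therefore follow-up frailty, and intervention can only be the between-arm term. Section 12 contains no paired or within-person analysis.

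**Step 5: sizing the next study.** Let Δ_A be the mean change in Group A and Δ_B the change that Group B would have shown. The planned contrast is τ = Δ_A − Δ_B. Using Δ_A for τ makes an error of exactly Δ_B, which was never observed. Group B was an active arm (Section 7: smartphone self-monitoring, one individual session, self-study materials, monthly calls), so Δ_B could be an improvement. Pandemic disruption could make it a worsening. The documents fix neither sign nor size.

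**Step 6: what 20 people can give.**
- Mean change: the 95% half-width is t(0.975, n−1)/√n = 2.093/4.472 = 0.47 SD of the change at n = 20. If only 16 or 12 had follow-up (assumed), it is 0.53 or 0.64 SD.
- Share improved: exact 95% intervals are 8.7% to 49.1% for 5/20 and 27.2% to 72.8% for 10/20 (illustrative counts).
- Variance, assuming normal data: (n−1)/χ² limits = 19/32.85 to 19/8.91, or 0.58 to 2.13 times the estimate. For a mean difference, required sample size is proportional to variance and has the same range.

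**Step 7: allocation order.** Each set of ten in Section 10.1 holds one arm, and Group A starts first. This does not fit a block table that allocates 40 people between two arms as they enter.

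**The case against.** **The change is disclosed.** This stands for Sections 7 and 10.1. Keeping the original text and adding a dated note appears to be how this form is amended, and both allocation passages point to those notes. A reader might infer that the document hides the loss of Group B; it does not. But the disclosure does not reach Section 12, or the trial description in Sections 2 and 5.3.

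**It is a pilot.** Pilot status excuses low power. It does not help here, because the term cannot be estimated at all.

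**The study still meets its aim.** This stands in part: Section 3 puts feasibility first, and Group A can inform it. It fails for the comparison of preliminary efficacy in Section 2.

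**The A-first order proves little.** A reader might infer that no random mechanism was ever used. The documents do not settle this. The sentence mentions a computer program, and four single-arm sets put in random order would come out A, A, B, B with probability 1/6. Randomising all 40 in advance is conceivable, though the text speaks of future participants. The fair reading is that arm was tied to enrolment time before COVID-19. It is also tempting to calculate how far a time trend would have inflated the standard error. That would describe a 40-person trial that did not take place and a time adjustment that Section 12 never planned. It would also assume equal cohorts of ten, although Section 8.6 plans 4 to 8 per group.

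**The next trial would be too small.** A reader might infer a definite shortfall. That needs the share of change that would also occur under Group B's active programme, and the documents give no figure for it.

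**Follow-up was delayed for eight people.** The 04.12.20 text is a plan. Whether assessments were postponed, and for how long, is not reported.

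**Conclusion.** The point holds and must be fixed. With 20 versus 0, the primary POCL model, its interactions and the linear models cannot estimate an intervention effect, and the plan offers no single-arm alternative. This rests on reading the 10.20.20 updates as zero Group B participants; it does not depend on the assumed coding of covariates.

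The no-impact statement is unsupported for between-group efficacy but may stand for feasibility. What remains is uncontrolled before-after change, mixed with time and pandemic disruption. The direction and size of the error from using it to plan a larger study cannot be determined from the documents.

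The mismatch between the A-first order and block randomisation is real but secondary. It can now only be described.

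**What to change.** By dated amendment, with the original text kept visible:

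1. **Section 12.** Replace every model that has an intervention term by within-person change from baseline with 95% confidence intervals. For frailty category, give the 3×3 baseline-by-follow-up table and the shares improved and worsened with exact intervals. For frailty score, SPPB, PROMIS, HbA1c, fasting glucose and BMI, use a paired method suited to each scale. Label the analysis post hoc, since it is written after Group A finished. Report the number with follow-up for each outcome and how missing follow-up is handled (Section 10.2 itself expects attrition). Give the date and mode of each end-of-study measurement: face-to-face, virtual or home kit.
2. **Sections 2, 5, 7 and 10.1.** Describe the study as conducted as a single-arm pre-post pilot, with one sentence stating the A-first order. Limit the no-impact statement by adding that between-group efficacy cannot be assessed.
3. **Sections 12.2 and 12.4.** Do not use the before-after change as a between-group effect size. Carry forward feasibility rates, and outcome variability only with its confidence interval.

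**Cost.** Wording and analysis text only; no new participants, visits or measurements. The downside is that the study can no longer be presented as a randomised trial or supply a controlled effect size.

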again before the focus group that their responses will be audio-recorded. Participants will be informed that no personally identifiable information will be discussed or recorded as part of the focus groups, and that questions will be centered on improving the program and evaluating its successes and areas for improvement. Risks of the focus groups would include discomfort answering questions and/or discomfort from participating in a group setting and breach of confidentiality. Participants do not have to answer or discuss any questions that make them uncomfortable, and that confidentiality will be protected by maintaining the audio recordings in a secure, locked location. The PI will conduct the focus group using the following questionnaires.

Focus Group Questions

As we are currently going through lifestyle changes due to the corona virus, tell me the impact of it on your day to day on self-monitoring of diet, physical activity, and diabetes management. (04.12.20)

What behavioral strategies have been most helpful to you in making the changes?

Behavioral strategies that have worked for you?

Behavioral strategies that have not work for you?

What are your plans for staying on track in the absence of these group sessions?

Since joining the program, what are the health-related benefits that you have experienced? Since joining the program, what are the appearance-related benefits that you have experienced? How would you say these benefits have influenced your quality of life?

8.7 Attach a Schedule of Activities (SOA) Excel File [Download the Template here: Schedule of Activities]	Check to indicate that the SOA Excel File is attached \rightarrow	\boxtimes
---	--	-------------

9. Preparation/Handling/ Storage/Accountability of Investigational Drug, Biologic, or Device

 \boxtimes *N/A* - *This study does not include any investigational products (e.g. drugs, devices or biologics)*

 \boxtimes N/A - An Investigator Brochure is attached

 \bowtie N/A - A Drug/Device Manual is attached

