After discussing with IRB person and mentors, we decided to not to enroll participants for the Group B due to highrisk for COVID-19. We were able to receive enough information from the Group A intervention participants and to finish enrolling participants for the pilot study. Modification due to Pandemic, forgoing control arm, and worked with the interventional participants still worked with the study data to meet study aim-the deviation related to COVID-19 did not impact subject rights, safety, welfare, or the overall integrity of the science of the study.

7

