12.4. Statistical Analyses

Include analysis of primary efficacy endpoints, secondary endpoints, safety analyses, and any planned interim analyses

The impact of the intervention on frailty status (non-frail, pre-frail, frail) and frailty score (0, 1, 2, 3, 4, or 5) over the 6month period (from baseline to follow-up) will be assessed by proportional odds cumulative logit (POCL) model to assess the log-odds of frailty as an indicator of being exposed to the intervention. The initial POCL model will adjust only for the baseline value of frailty status. A subsequent model will adjust for baseline age, sex, ethnic group, BMI, and Hba1c, to determine potential covariate interactions with the intervention. Continuous secondary outcomes including fasting glucose, Hba1c, and BMI will be assessed using linear regression with intervention, baseline frailty, sex, and ethnic group as categorical predictor variables and baseline age, BMI, and Hba1c as continuous predictor variables. The categorical outcomes SPPB and PROMIS scores will also be evaluated using the POCL model. Because the POCL model is complex and this is a pilot study, it is not practical or feasible to do a power analysis for the given experimental design but based on the work of Drs. [name] and [name], we believe at least 20 participants in the group (mHealth+ group Intervention group) are needed. The effect of the intervention on the change in frailty category and/or frailty scores will be used to calculate power and sample size estimation for a future, larger study.

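### At least 12 of the 20 treated participants (possibly all 20) spent part of their six months under the distancing order; with no control arm and no account of exposure, their change from baseline cannot be read as the effect of the intervention

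*Combined protocol and SAP*

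**What the plan says.** Section 5.3 sets the design: "This will be a 6-month randomized controlled trial". The update of 04.12.20 in Section 7 refers to a distancing order already in force and to "eight participants who are finishing the study on April 20, 2020". It adds: "Our next study group will finish the study in 2nd week of June, 2020". It also says that remaining sessions will be virtual, that enrolment is paused, and that the April finishers' in-person blood tests and frailty assessments will wait until the order lifts.

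The 10.20.20 updates in Section 10.1 report that "we finished our participants (N=20) in the group intervention", and that "we completed up to three face to face group intervention sessions (Group A) over WebEx due to COVID-19 restrictions". They also report that Group B was not enrolled. The statement on integrity ("deviation related to COVID-19 did not impact subject rights, safety, welfare, or the overall integrity of the science of the study") appears there and in Section 7.

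Section 8.6 makes low physical activity one of the five frailty characteristics. It also adds a focus-group question, dated 04.12.20, asking participants about the pandemic: "tell me the impact of it on your day to day on self-monitoring of diet, physical activity, and diabetes management".

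Section 12.4, repeated in Section 12.3, still names its target as "The impact of the intervention on frailty status (non-frail, pre-frail, frail) and frailty score (0, 1, 2, 3, 4, or 5". The first model adjusts for baseline frailty, and the second for baseline age, sex, ethnic group, BMI and HbA1c. Neither has a term for cohort, calendar period or delivery mode. Section 12.2 uses the resulting effect to size a larger study.

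**The concern.** The order bore on the behaviours that the programme tries to change, and it altered how part of the programme was delivered. The added focus-group question shows that the investigators thought this possible.

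With one arm, programme and pandemic move together within each exposed participant. If activity fell under the order, the low-activity item worsens and the programme looks weaker than it is. If time at home improved diet or logging, it looks stronger. Either way the change from baseline describes the programme plus the restrictions, and Section 12.2 would carry that mixture into the next trial as an intervention effect.

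**Working it through.** **The plan's own figure.** Section 12.2 asks for at least 20 in the group arm but gives no effect size, SD, alpha or power, so it cannot be reproduced. The counts do agree internally: 10 + 10 = 20 in Group A (Section 10.1), and 3 + 4 + 3 = 10 sessions (Section 7). The plan gives no count of exposed participants.

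**Inputs.**
- 20 participants finished (Section 10.1).
- Window of 6 months, taken as 183 days (Section 5.3).
- 8 participants ending 20 April 2020; the next group ending in the second week of June, taken as 8-14 June (Section 7).
- 4-8 people per session group (Section 8.6). The size of the June group is not stated.
- Order in force by 12 April 2020; its start and end dates are not given (Section 7).

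**Step 1: how many were exposed.** Exposed = 8 + June group = 8 + 4 to 8 + 8 = 12 to 16, or 60-80% of 20. The remaining 20 - 16 = 4 to 20 - 12 = 8 people have no dates. They may have finished earlier or belonged to a later group. The limit of three online sessions does not settle this, because months 4-6 contain exactly three monthly sessions. A group starting in mid-January 2020 would have had all three online and been exposed throughout those months. The supportable range is therefore 12-20 exposed and 0-8 unexposed.

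**Step 2: how much of the window.** Overlap = end date - 12 April.
- April cohort: 20 April - 12 April = 8 days; 8/183 = 4%.
- June cohort: 8 to 14 June - 12 April = 57 to 63 days; 31-34%. This takes the order as still in force when they finished.
- If the order is assumed to have begun between 12 March and 12 April: 8-39 days (4-21%) for April, and about 60-91 days (33-50%) for June, using 11 June as the end.

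The April cohort's frailty assessment was deferred until the order lifted, so its exposure before the primary measurement exceeds these figures by an unstated amount.

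**Step 3: what an effect could do.** These are illustrations; the documents give no rate or SD.
- One participant newly meeting, or ceasing to meet, one item moves the mean 0-5 score by 1/20 = 0.05. One item takes a person from non-frail to pre-frail (0 to 1) or from pre-frail to frail (2 to 3).
- Assume that 10-30% of those affected change on the low-activity item. If only the June cohort is affected, the shift is 4/20 x 0.10 = 0.02 to 8/20 x 0.30 = 0.12. If all exposed are affected alike, it is 12/20 x 0.10 = 0.06 to 20/20 x 0.30 = 0.30. The sign is unknown.
- On a standardised change score, assume a 0.5 SD pandemic shift and no programme effect. The pooled mean moves by (exposed/20) x 0.5 = 0.30, 0.40 or 0.50 SD for 12, 16 or 20 exposed. A two-sided 5% pre-post z-test has statistic mean (shift x √20), so it would be significant about 27%, 43% or 61% of the time.

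**Step 4: can the analysis separate the two?** Every analysed participant is in Group A, so the intervention indicator is constant and its coefficient cannot be estimated. What remains is a change from baseline.

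A split by exposure would not rescue it. The difference detectable with 80% power is (1.96 + 0.84) x √(1/exposed + 1/unexposed). That is 1.28 SD for 12 v 8, 1.37 SD for 14 v 6 and 1.57 SD for 16 v 4. With 20 exposed there is no comparison at all.

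**The case against.** The strongest reply is that the basic defect is the loss of Group B, and that confounding with the pandemic follows from it. That is right. Section 12.4 specifies a two-arm contrast, not a pooled pre-post effect. But the plan was not revised when Group B was dropped, and change from baseline is now the only quantity it can deliver.

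A second reply is that the integrity sentence concerns forgoing the control arm. It does open there, so it should not be read as a claim that participants' behaviour was unaffected. Its wording nevertheless reaches the science of the whole study, and readers will take it that way.

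A third is that this is a pilot with a feasibility aim, and that the online sessions and the focus-group question are disclosed. That limits the seriousness. The disclosure is narrative, however, and does not reach the analysis.

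Stronger readings are tempting, but the documents do not support them:
- *Some cohorts were exposed and earlier ones were spared.* No cohort is recorded as finishing before the order.
- *Both dated cohorts spent months 4-6 under the order.* For April the dated overlap is 8 days, and the update identifies only its tenth session as virtual. Even for June it is about two months.
- *The order hid a given share of the programme's effect.* Any such figure needs an assumed rate, direction and true effect, and would have to treat 8 days and two months alike.

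**Conclusion.** The point holds as a limit on interpretation that the plan should state. At least 12 of 20 participants, and possibly all 20, had part of their window under the order. The floor of 12 assumes that the June group was a single group of at least the planned minimum of 4. The group sizes of 4-8 also sit uneasily with the 10 + 10 layout in Section 10.1, so 16 is not a ceiling.

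Exposure was uneven between cohorts. The documents show that an effect on diet, activity and diabetes management was thought possible; they do not show one, and the shifts in Step 3 are assumptions. What does not depend on them is that no concurrent comparison exists, so the baseline-to-follow-up change is not an estimate of the intervention's impact, and the assurance about the science is broader than the design can support.

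**What to change.** 1. **Section 12.4 (and 12.3).** From existing dates and session records, code for each participant the days of the 6-month window under the order, the days under the order up to the frailty assessment, and the number of WebEx sessions. Report change in frailty score (with and without the low-activity item), HbA1c, BMI and PROMIS descriptively by cohort and exposure.
2. **Sections 7 and 10.1.** Replace the integrity statement with one saying that the observed change is uncontrolled and that, for exposed cohorts, it reflects the programme together with pandemic restrictions.
3. **Section 12.2 (and its repeat in 12.4).** Where the pooled change informs the future study, label it a descriptive, pandemic-affected pre-post change and not an intervention effect. Do not size that study on a range between exposed and unexposed participants: there may be only 0-8 unexposed people, and any such contrast is also confounded with cohort and season.

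The cost is revised wording and a few descriptive tables from data already held, with no new collection. The drawback is that the strata are small and one may be empty, so the tables can describe but not test.
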